### 3.6.2 Adverse Events of Special Interest

Hepatic function abnormality meeting the definition of Hy's law is considered an adverse event of special interest. Number and proportion of subjects who meet Hy's law criteria: aspartate transaminase or alanine transaminase  $\geq 3 \times$  upper limit of normal range (ULN) together with total bilirubin  $\geq 2 \times$  ULN will be summarized by treatment.

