3. **Reduced BP after exposure to known allergen for that patient (minutes to several hours):**
 - a. Infants and children: low systolic BP (age specific) or greater than 30% decrease in systolic BP
 - b. Adults: systolic BP of less than 90 mm Hg or greater than 30% decrease from that person's baseline

Reference:

10.5 Appendix 5 - Actions Required in Cases of Increases in Liver Biochemistry and Evaluation of Hy's law

Introduction

This Appendix describes the process to be followed in order to identify and appropriately report cases of Hy's Law (HL). It is not intended to be a comprehensive guide to the management of elevated liver biochemistries.

During the course of the study the investigator will remain vigilant for increases in liver biochemistry. The investigator is responsible for determining whether a subject meets potential Hy's Law (PHL) criteria at any point during the study.

The investigator participates, together with MedImmune clinical project representatives, in review and assessment of cases meeting PHL criteria to agree whether HL criteria are met. HL criteria are met if there is no alternative explanation for the elevations in liver biochemistry other than Drug Induced Liver Injury (DILI) caused by the investigational product.

The investigator is responsible for recording data pertaining to PHL/HL cases and for reporting AEs and SAEs according to the outcome of the review and assessment in line with standard safety reporting processes.

Definitions

Potential Hy's Law (PHL)

Aspartate aminotransferase (AST) or alanine aminotransferase (ALT) $\geq 3 \times$ upper limit of normal (ULN) together with TBL $\geq 2 \times$ ULN at any point during the study following the start of investigational product irrespective of an increase in alkaline phosphatase (ALP).

Hy's Law (HL)

AST or ALT $\geq 3 \times$ ULN together with TBL $\geq 2 \times$ ULN, where no other reason, other than the investigational product, can be found to explain the combination of increases; eg, elevated ALP indicating cholestasis, viral hepatitis, another drug.

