For PHL and HL the elevation in transaminases must precede or be coincident with (ie, on the same day) the elevation in TBL, but there is no specified timeframe within which the elevations in transaminases and TBL must occur.

Identification of Potential Hy's Law Cases

In order to identify cases of PHL it is important to perform a comprehensive review of laboratory data for any subject who meets any of the following identification criteria in isolation or in combination:

- $ALT \geq 3 \times ULN$
- $AST \geq 3 \times ULN$
- $TBL \geq 2 \times ULN$

The investigator will without delay review each new laboratory report and if the identification criteria are met will:

- Notify the sponsor study representative
- Determine whether the subject meets PHL criteria by reviewing laboratory reports from all previous visits
- Promptly enter the laboratory data into the laboratory eCRF

Follow-up

Potential Hy's Law Criteria Are Not Met

If the subject does not meet PHL criteria the investigator will:

- Inform the sponsor representative that the subject has not met PHL criteria
- Perform follow-up on subsequent laboratory results according to the guidance provided in the CSP.

Potential Hy's Law Criteria Are Met

If the subject does meet PHL criteria the investigator will notify the sponsor study representative who will then inform the central study team. The study Physician contacts the investigator, to provide guidance, discuss and agree an approach for the study subjects' follow-up and the continuous review of data. Subsequent to this contact the investigator will:

- Monitor the subject until liver biochemistry parameters and appropriate clinical symptoms and signs return to normal or baseline levels, or as long as medically indicated
- Investigate the etiology of the event and perform diagnostic investigations as discussed with the study physician.

- Complete the Liver eCRF Modules as information becomes available
- If at any time (in consultation with the Medical Monitor) the PHL case meets serious criteria, report it as an SAE using standard reporting procedures

Review and Assessment of Potential Hy's Law Cases

The instructions in this section should be followed for all cases where PHL criteria are met.

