No later than 3 weeks after the biochemistry abnormality was initially detected, the Medical Monitor will contact the investigator in order to review available data and agree on whether there is an alternative explanation for meeting PHL criteria other than DILI caused by the investigational product. The Clinical Medical Monitor and Global Safety Physician will also be involved in this review together with other subject matter experts as appropriate.

According to the outcome of the review and assessment, the investigator will follow the instructions below.

If there is an agreed alternative explanation for the ALT or AST and TBL elevations, a determination of whether the alternative explanation is an AE will be made and subsequently whether the AE meets the criteria for a SAE:

- If the alternative explanation is not an AE, record the alternative explanation on the appropriate eCRF
- If the alternative explanation is an AE/SAE, record the AE /SAE in the eCRF accordingly and follow the sponsor standard processes

If it is agreed that there is no explanation that would explain the ALT or AST and TBL elevations other than the investigational product:

- Report an SAE (report term 'Hy's Law') according to sponsor standard processes.
 - The 'Medically Important' serious criterion should be used if no other serious criteria apply
 - As there is no alternative explanation for the HL case, a causality assessment of 'related' should be assigned.

If, there is an unavoidable delay, of over 3 weeks, in obtaining the information necessary to assess whether or not the case meets the criteria for HL, then it is assumed that there is no alternative explanation until such time as an informed decision can be made:

- Report an SAE (report term ‘Potential Hy’s Law’) applying serious criteria and causality assessment as per above
- Continue follow-up and review according to agreed plan. Once the necessary supplementary information is obtained, repeat the review and assessment to determine whether HL criteria are met. Update the SAE report according to the outcome of the review

References:

FDA Guidance for Industry (issued July 2009) ‘Drug-induced liver injury: Premarketing clinical evaluation’: <http://www.fda.gov/downloads/Drugs/GuidanceComplianceRegulatoryInformation/Guidances/UCM174090.pdf>

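### SAP 3.6.2 gives the name Hy's law to the thresholds that the protocol calls potential Hy's law, and omits the alternative-explanation condition and the ordering rule

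*SAP*

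**What the plan says.** SAP 3.6.2 states that a hepatic function abnormality meeting the Hy's law definition "is considered an adverse event of special interest". It then plans a summary by treatment of the "Number and proportion of subjects who meet" Hy's law criteria, and gives those criteria as two laboratory thresholds: AST or ALT at least 3 times ULN, and total bilirubin (TBL) at least 2 times ULN. The section says nothing more about the definition.

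Protocol Section 5.3.1 makes hepatic function abnormalities the study's only adverse event of special interest (AESI) and refers to Section 5.6.2 and Appendix 10.5 for the definition. Appendix 10.5 sets up two categories:

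- Potential Hy's law is the same pair of thresholds, reached after investigational product has started, whatever the alkaline phosphatase.
- Hy's law is that finding "where no other reason, other than the investigational product, can be found to explain the combination of increases". Investigator and sponsor decide this in a joint review of the potential cases: "HL criteria are met if there is no alternative explanation for the elevations in liver biochemistry" other than injury caused by the investigational product.

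A further rule covers both categories: "For PHL and HL the elevation in transaminases must precede or be coincident with (ie, on the same day) the elevation in TBL". No time limit between the two elevations is set.

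**The concern.** The two documents use one name for different things. In the protocol, Hy's law is the result of a causality review. In SAP 3.6.2 it is a laboratory screen, and that screen is the protocol's potential Hy's law without its timing conditions.

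What is at stake is the consistency of the safety report. A case with an agreed alternative cause is recorded under that cause in the adverse event data, while the AESI table would still list the subject as meeting Hy's law criteria. With events this rare, one such subject could make up the whole content of the table. Other causes are possible in this population: exclusion criterion 13 in Section 4.1.3 allows nonalcoholic steatohepatitis or fatty liver disease without portal hypertension or cirrhosis.

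**Working it through.** The plan states no figure to reproduce, and the point depends on no rate, power or sample size. The check is a comparison of texts.

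| Element | SAP 3.6.2, Hy's law criteria | Appendix 10.5, potential Hy's law | Appendix 10.5, Hy's law |
|---|---|---|---|
| AST or ALT ≥3 × ULN and TBL ≥2 × ULN | Required | Required | Required |
| After start of investigational product | Not stated | Required | Follows, because it is decided among potential cases |
| Transaminase rise on or before TBL rise | Not stated | Required | Required |
| Time window between the two rises | Not stated | None set | None set |
| No other explanation, agreed in review | Not stated | Not required | Required |

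The SAP column differs from the Hy's law column on the condition that defines Hy's law. It also falls short of the potential Hy's law column on timing.

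Four hypothetical subjects show the effect. Scheduled post-dose serum chemistry falls on Days 7, 14, 22 and 28 and at the end-of-study visit (Tables 4.2.3-1 and 4.2.4-1).

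1. Both thresholds are met on the same day and no other cause is found. Protocol: Hy's law. SAP: counted. The two agree.
2. Both thresholds are met on the same day, and the review agrees that another drug is the cause. Protocol: potential Hy's law only. SAP: counted as Hy's law.
3. TBL crosses its threshold on Day 14 and stays up; ALT first crosses on Day 22. Protocol: neither category, because bilirubin rose first. SAP: both values are raised on Day 22, and nothing in 3.6.2 excludes the subject.
4. ALT crosses on Day 7 and settles; TBL crosses on Day 14. Protocol: potential Hy's law at least, since the order is right and there is no time limit. SAP: depends on whether the two values must come from the same sample, which 3.6.2 does not say.

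Subjects 2 and 3 are over-counted under the Hy's law name. Subject 4 could be missed.

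The SAP's wording that the two elevations occur together does not supply the ordering rule. Appendix 10.5 joins the thresholds in the same way in its own definitions and still states the order as a separate requirement.

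**The case against.** The strongest reply is that the count itself is sound and only its label is loose. Protocol Section 5.6.2 cites the same bare thresholds for the liver AESI without a causality condition, and Section 5.3.1 does not limit the AESI to adjudicated cases. The SAP prints the thresholds beside the label, so a careful reader can see that it is a laboratory count. This largely stands, and it is why the point is low priority. It does not remove the conflict. Section 5.6.2 says only that such cases may need SAE reporting, does not call them Hy's law, and refers to Appendix 10.5. It is the SAP that ties the AESI to the Hy's law definition.

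A second reply is that the ordering rule will seldom matter. Section 4.3.3 requires the liver tests to be run and assessed concurrently, and same-day elevation satisfies the rule. That is fair: the omission matters only when the two elevations first appear at different draws.

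A third is that the statistical programming plan (SPP), which SAP Section 1 says holds table templates and specifications, may carry the missing rules. It is not among the documents reviewed, so this cannot be excluded. The wording of SAP 3.6.2 would still differ from the protocol.

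A fourth is that significant hepatic disease, raised liver tests and positive hepatitis B or C serology at screening are excluded, and dosing lasts 28 days, so the table may well be empty. This stands.

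**Conclusion.** The point holds as a definitional mismatch in one descriptive safety table. Followed as written, SAP 3.6.2 could place under the Hy's law name a subject whom the protocol classes as potential Hy's law only, or as neither. No endpoint, test or subject-management step is affected.

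The documents give no event rate. That few or no cases will occur in 46 subjects is a judgement, not a calculation. One subject is 1/23 = 4.3% of an arm, but that is true of any single subject and does not measure likely effect.

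A reader might infer two stronger conclusions, and the documents support neither:

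- That a case with another cause would be reported to the sponsor as Hy's law. Appendix 10.5 prevents this: "If there is an agreed alternative explanation for the ALT or AST and TBL elevations", the case is recorded under that explanation, and the SAE term Hy's Law is kept for cases with none. If the review is unavoidably delayed beyond 3 weeks, the interim SAE term is Potential Hy's Law.
- That the table drives decisions about the development programme. The nearest text, protocol Section 4.4, gives Hy's law liver changes as one example of a reason to suspend or terminate this study. That is a decision taken during conduct, there is no planned interim analysis, and nothing links the decision to the SAP 3.6.2 table.

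The conclusion assumes that the SPP does not already separate the two categories.

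**What to change.** In SAP 3.6.2, report two rows by treatment:

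- **Potential Hy's law:** the existing laboratory thresholds, counted after the first dose of investigational product, with the transaminase elevation before or on the same day as the TBL elevation and no limit on the interval between them, as in Appendix 10.5.
- **Hy's law:** the cases agreed as such in the Appendix 10.5 review.

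Refer to Appendix 10.5 for both definitions, and carry the same rules into the SPP. The cost is SAP wording and one extra table row. No new data are needed, because the protocol's own review already produces both classifications.

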#### 3.6.3 Deaths and Treatment Discontinuations due to Adverse Events

Death and AEs resulting in permanent discontinuation from the study drug will be summarized by treatment. The summary includes overall, categorized by MedDRA system organ class, and preferred term.

#### 3.6.4 Clinical Laboratory Evaluation

Hematology, serum chemistry, and urinalysis laboratory evaluations will be performed during the study. The hematology and serum chemistry (including amylase, lipase, lactate, and calcitonin) parameters as well as their changes from baseline will be summarized with descriptive statistics (number of subjects, mean, and standard deviation, median, minimum and maximum) by treatment group at each time point. The urinalysis results will be listed. The hematology and serum chemistry results will also be classified as low, normal, or high. The urinalysis results will be classified as normal or abnormal. The shift from baseline hematology, serum chemistry, and urinalysis results will be summarized by treatment group at each time point.

### 3.6.5 Other Safety Evaluations

#### **3.6.5.1 Vital Signs**

Vital signs including pulse rate (beats/min), blood pressure (mm Hg), temperature (°C), and respiratory rate (breaths/min), as well as the change from baseline for each of those parameters will be descriptively summarized by treatment group at each time point.

The 24-hour average ambulatory blood pressure monitoring (ABPM) pulse rate (beats/min) and systolic and diastolic blood pressure (mm Hg) from the ABPM will be summarized by treatment group at each time point. The change from baseline (Day -2) for the 24-hour average pulse rate and systolic and diastolic blood pressure at each post-baseline visit will be analyzed with an analysis of covariance with an effect for treatment and the baseline value as the covariate. The above summary and analyses will also be conducted for pulse rate, systolic blood pressure, and diastolic blood pressure during asleep and awake periods.

#### 3.6.5.2 Electrocardiogram

Electrocardiogram parameters will be assessed using standard 12-lead electrocardiography. The following Electrocardiogram (ECG) parameters as well as the change from baseline for each of those parameters will be reported and descriptively summarized by treatment group at each of the specified time points: Heart rate (beats/min), RR (msec), PR (msec), QRS (msec), and QT (msec) intervals and the QT corrected interval.

The normality/abnormality of the ECG evaluation will be summarized using frequency tables of the number of subjects with a normal/abnormal ECG evaluation at each scheduled visit.

#### 3.8 Pharmacokinetics

For MEDI0382, Dapagliflozin and β-hydroxybutyrate, actual time of sampling, rather than nominal (planned) sampling time, will be used to derive PK parameters. Nominal sampling time will be used for the summary of PK concentrations and will be utilized in the descriptive summaries in mean plots. Missing PK parameters will not be imputed.

For subjects in each treatment group the following pharmacokinetic parameters will be determined from the plasma concentration-time data for MEDI0382, dapagliflozin and  $\beta$ -hydroxybutyrate if data allow. The pharmacokinetic parameters will be calculated by standard non-compartmental analysis according to current working practices and using Phoenix WinNonlin 6.3 or equivalent:

1. Cmax: The first occurrence of the maximum observed plasma concentration determined directly from the raw concentration-time data

- 2. tmax: The first time at which Cmax is observed will be determined directly from the raw concentration-time data.
- 3. Cτ: trough concentrations from the plasma concentration-time data at the end of the dosing interval (i.e. 24 hours).
- 4. AUCτ: Area under the plasma concentration time curve at the end of the dosage interval τ.
- 5. Ro: observed accumulation ratio will be calculated using both the AUC and Ctrough methods, where data allows, as follows: Ro = AUCτdayi/AUCτday1 and Ro = Cτdayi/Cτday1.

If data allows additional parameters may be derived for MEDI0382 and Dapagliflozin such as t half: the apparent terminal elimination half-life ( $t_{1/2}$ ) obtained as the ratio of  $ln2/\lambda_z$ , where  $\lambda_z$  is the terminal phase rate constant estimated by linear regression analysis of the log transformed concentration-time data; and Cl/F: the apparent clearance calculated as  $CL/F=Dose/AUC(0-\infty)$ .

All the derived parameters described above will be listed. For each of these parameters, except for tmax, the following summary statistics will be calculated for each active treatment group: median, maximum, minimum, arithmetic mean, standard deviation, CV, geometric mean. For tmax, the following summary statistics will be calculated for each active treatment group: median, maximum, minimum, arithmetic mean.

Individual Ctrough will be listed by treatment and day and will be summarized as maximum, minimum, arithmetic mean and geometric mean.

Subjects who have at least one measurable concentration time point of investigational product will be used for this analysis.

### 4 INTERIM ANALYSIS

No interim analysis is planned.

#### 5 VERSION HISTORY

Version	Date	Summary of Changes	Reason for Change
1.0	03JUL2018	Initial document	Initial document

